7.5.1 Fixed sample size

The number of DL users from each country has been estimated based on national drug sale statistics (Annex 1A). The annual unique number of DL users in Denmark, Finland, and Sweden for age groups 0–4, 5–19, 20–64, and ≥ 65 years is estimated to be 20,000, 86,000, 215,000, and 44,500, respectively. Data for Norway on DL prescriptions and seizures/SVT/A-fib/flu are available for a shorter time period; and therefore, Norway is not included in the calculations of the minimum detectable IRR. The number of annual unique DL users in the four countries is thereby slightly underestimated.

7.5.2 Proportion of current and non-current exposure time among DL users for the purpose of calculation of minimum detectable IRR

DL exposure (i.e., current DL use) is time-varying, and each person might have one or more periods as exposed and one or more periods as unexposed. Individuals in the study population (i.e., individuals who have redeemed at least one prescription of DL) are assumed to be exposed in a period following the date of DL purchase (i.e., current users). An estimate of the number of DL prescriptions redeemed per year in each age group was obtained from the feasibility study performed prior to developing the synopsis and the present protocol. For the minimum detectable IRR calculations, the mean number of prescriptions in each age group per year from the Danish data is used as an estimate of the average annual number of redemptions. The exposure period is then calculated as follows: (mean annual number of prescriptions in each age group*4 weeks (standard days' supply)) + 4 weeks grace period to account for intermittent use and a possible wash-out effect. Beyond this period, individuals are assumed to be unexposed (i.e., non-current users). The average number of prescriptions per year was estimated to be 1.50, 1.62, 1.78, and 2.30 for age groups 0–4, 5–19, 20–64, and ≥65 years, respectively¹.

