Exposure periods for age groups 0–4, 5–19, 20–64, and ≥65 years were then calculated to be 10.00, 10.48, 11.12, 13.20 weeks, respectively. The proportion of exposed time in each age group is calculated as number of weeks exposed divided by number of weeks in a year (i.e., 52 weeks). For example, for age group 0–4 years, the proportion of exposed time is 10 weeks/52 weeks = 19%, and thus, the proportion of non-exposed or neither exposed nor unexposed time is 81%. Note: A simplified method was used to calculate exposed and unexposed person time for each age group for the purpose of estimating the minimum detectable IRR. The method for calculating exposed, unexposed, and neither exposed nor unexposed time for individuals for the study analysis is outlined in section 7.3.1.

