7.5.3 Background event rate

The background incidence rate (i.e., IR) of seizures, SVT, and A-fib/flu was obtained from published studies [Hauser, W. A. and Beghi, E. 2008] [Orejarena, L. A., et al 1998] [Wilke, T., et al 2013]. IRs of seizure among unexposed individuals for age groups 0–4, 5–19, 20–64, and ≥65 years were estimated to be 65, 50, 40, and 40 per 100,000 person-years, respectively [Hauser, W. A. and Beghi, E. 2008]. The IR of SVT is reported to be 13/100,000 person-years for persons aged 19 years or younger, 27/100,000 person-years for persons aged 20–64

¹ By using Danish figures we might get conservative estimates of the minimal detectable IRR as mean number of prescriptions calculated for the feasibility study showed slightly lower means for Denmark compared to Sweden (figures from Finland and Norway were not available for these calculations). The average number of prescriptions per age group for the 20-64 and ≥65 year's age groups was calculated as the mean number of annual prescriptions (2001-2012) per age group using data from Denmark for ages ≥16 years. For the 5-19 year age group, the calculation was based on data from Denmark for ages 16-19. For the 0-4 year age group, the calculation was based on Swedish data from the feasibility study, which showed a tendency for a lower number of prescriptions in this age group compared to the older age groups.

years, and 122/100,000 person-years for persons aged 65 years or older [Orejarena, L. A., et al 1998]. Wilke et al. (2013) [Wilke, T., et al 2013] reported the incidence of A-fib to increase markedly with age with 0.0016 cases/1000 person-years in children (<15 years) and approximately 30 cases/1000 person-years for persons aged 80 years or older. No data on the epidemiology of flutter were available.

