7.5.6 Example of calculating the minimum detectable IRR

The mean number of DL prescriptions in the age group 0–4 years is 1.50 prescriptions. This gives an exposure period of $(1.50 * 4 \text{ weeks}) + 4 \text{ weeks} = 10 \text{ weeks}$. In this age group, 20,000 children have redeemed DL (i.e., the fixed sample size for this age group). Due to the exposure period of 10 weeks in this group, the proportion of the time exposed to DL is $10 \text{ weeks} / 52 \text{ weeks per year} = 19\%$. The background annual rate of seizures is 65/100,000 in this age group. It is assumed that individuals in this age group will be included in the study for an average of 2 years. When using a 1-sided test, significance level of 5% and power of 80%, the minimum detectable IRR will be 3.0.

Table 6 The minimum detectable incidence rate ratio (IRR>1) was calculated based on the Nordic population of SL users with at least one prescription of DL per year. Incidence rate (IR) of seizures is based on Hauser & Beghi (2008) [Hauser, W. A. and Beghi, E. 2008]. A 1-sided test, significance level of 5% and power of 80% have been used.

Age group (years)	Annual IR of seizures among unexposed individuals per 100,000 person-years	Mean number of individuals with at least one annual DL prescription in the Nordic countries	Estimated number of weeks exposed based on mean number of DL prescriptions per person	Minimum detectable IRR t=2 and 6 years (for age 0-4 years and age ≥5 years)
0-4	65	20,000	10.00	3.0
5-19	50	86,000	10.48	1.5
20-64	40	215,000	11.12	1.3
≥65	40	44,500	13.20	1.7

Table 7 The minimum detectable incidence rate ratio (IRR>1) was calculated based on the Nordic population of DL users with at least one prescription of DL per year. Incidence rate (IR) of SVT is based on Orejarena et al. (1998) [Orejarena, L. A., et al 1998]. A 1-sided test, significance level of 5% and power of 80% have been used.

Age group (years)	Annual IR of SVT among unexposed individuals per 100,000 person-years	Mean number of individuals with at least one annual DL prescription in the Nordic countries	Estimated number of weeks exposed based on mean number of DL prescriptions per person	Minimum detectable IRR t=2 and 6 years (for age 0-4 years and age ≥5 years)
0-4	13	20,000	10.00	8.2
5-19	13	86,000	10.48	2.1
20-64	27	215,000	11.12	1.4
≥65	122	44,500	13.20	1.4

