In Substudy 2B, seizure outcomes for which a drug overdose is also registered at the same hospitalization are excluded. In general, drug overdoses are likely to be underreported in the registries, as the registries often do not have sufficient detail to differentiate between overdoses from different types of drugs. Therefore, it is not possible to distinguish between overdoses from DL and overdoses from other drugs. Because overdoses of DL are rare compared to other drug overdoses, persons with any drug overdose registered during the same hospitalization as the seizure are excluded from analysis 2B. As a result, this study cannot determine whether the seizure outcomes are specifically associated with DL overdoses.

Sample size

Based on the assumptions made, the sample size is not adequate in the youngest age group for the assessment of the potential association between DL use and A-fib. Also, in this age group only relatively strong associations (IRR=8.2) can be properly assessed for the association between DL use and SVT.

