12.7 Annex 7 Minimum Detectable Incidence Rate Ratio Calculation

The minimum detectable incidence rate ratio (λ) was calculated based on Bryant & Morganstein [Bryant, E. 1987] and algebraically re-arranged to estimate $\lambda = \frac{p_1}{p_2}$:

$$(p_1 - p_2)^2 = (Z_\alpha + Z_\beta)^2 \left[\frac{p_1 q_1}{En} + \frac{p_2 q_2}{(1-E)n} \right]$$

where $\lambda = \frac{p_1}{p_2}$ is the minimum detectable incidence rate ratio

p_1 is the incidence rate of seizures (or supraventricular tachycardia (SVT) or atrial fibrillation/atrial flutter (A-fib/flu)) among current desloratadine (DL) users

p_2 is the incidence rate of seizures (or SVT or A-fib/flu) among non-current DL users

$q_1 = 1 - p_1$ and $q_2 = 1 - p_2$

Z_α is the significance level (type I error)

Z_β is type II error

n is the sample size (number of DL-ever-users)

E is proportion of the sample exposed to DL (i.e., proportion of weeks exposed to DL)

$1-E$ is the proportion of not exposed to DL

Patients are assumed to be followed for 2 years (ages 0-4 years) and 6 years (ages ≥ 5 years).

The incidence of seizures (or SVT or A-fib/flu) among non-current DL users during the follow-up period, t ($t=2$ years for children age 0-4 years, otherwise $t=6$ years) is calculated using the exponential model:

$$p_2 = 1 - \exp(-p_2' t)$$

Where p_2' is the annual incidence rate of seizures (or SVT or A-fib/flu) among non-current DL users (i.e., background event rate).

Based on the known size of the population in the specific age group (n) (e.g., number of children age 0-4 years who have redeemed at least one prescription of DL, $n=20,000$), the IR of seizures (or SVA) among non-current users ($p_2 = 1 - \exp(-65 \cdot 2/100000)$) and the proportion of the sample exposed to DL ($E = ((1.5 \cdot 4) + 4 \text{ weeks}) / 52 \text{ weeks} = 0.19$), the minimum detectable incidence rate ratio (λ) can be calculated.

Using an alternative sample size formula from Woodward, we obtained similar results .

12.8 Annex 8 Directed Acyclic Graphs (DAGs) for the study on Desloratadine and risk of first seizure, atrial fibrillation or flutter, and supraventricular tachycardia

Primary DAG meeting	
Date	06 January 2015
Organizer	ApEHR
Attendees	
NIPH PPD [REDACTED]
 
ApEHR PPD [REDACTED]
 
MSD PPD [REDACTED]
 
Clinical experts PPD [REDACTED]

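### Annex 7's unpooled two-proportion formula is conservative where few exposed events are expected, so several minimum detectable IRRs in Tables 6-8, including the 8.2 repeated in section 7.9, have more than the stated 80% power

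*Protocol*

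**What the plan says.** The sample is fixed, so section 7.5 reports minimum detectable incidence rate ratios instead of a sample size. Each of Tables 6-8 carries the same statement: "A 1-sided test, significance level of 5% and power of 80% have been used". Section 7.5.6 works one cell in full, seizures at 0-4 years, and concludes that "the minimum detectable IRR will be 3.0". Section 7.9 repeats the Table 7 value for SVT in the youngest group: "only relatively strong associations (IRR=8.2) can be properly assessed".

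Annex 7 gives the method, a normal-approximation formula for the difference of two proportions in which each group contributes its own variance. The split between groups is by time: "E is proportion of the sample exposed to DL (i.e., proportion of weeks exposed to DL". Annex 7 adds that a second sample size formula gave similar results. Section 7.5.2 describes its division of person-time as simplified. Nothing in the protocol discusses how the approximation behaves with very few events.

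**The concern.** The formula relies on approximate normality with the variance evaluated under the alternative. In the youngest groups, exposed time at the background rate would yield only a handful of events, and for SVT at 0-4 years about one. The time split is about 1:4. Under these conditions the stated 80% need not hold at the printed ratio. Section 7.9 uses one of these values to tell readers what the study can assess in small children, so the figure should carry the power it claims.

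**Working it through.** **Inputs, all from the protocol.**
- Users by age group (section 7.5.1): "20,000, 86,000, 215,000, and 44,500, respectively".
- Exposed weeks per year (section 7.5.2): "10.00, 10.48, 11.12, 13.20 weeks, respectively". Dividing by 52 gives E = 0.192, 0.202, 0.214 and 0.254.
- Follow-up t (Annex 7): "Patients are assumed to be followed for 2 years (ages 0-4 years) and 6 years" for ages 5 and over.
- Seizure rates (section 7.5.3): "65, 50, 40, and 40 per 100,000 person-years, respectively".
- SVT rate up to 19 years: 13 per 100,000 (Table 7). A-fib rate at 5-19 years: 3.8 per 100,000 (Table 8).
- One-sided 5%, 80% power, so Z values 1.645 and 0.842 and squared sum 6.183.

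**Step 1: reproduce the printed value for SVT 0-4.**
- p2 = 1 − exp(−13 × 2/100,000) = 0.00025997.
- En = 0.1923 × 20,000 = 3,846 and (1−E)n = 16,154.
- Try λ = 8.227, so p1 = 0.0021388. Left side: (p1 − p2)² = 3.53 × 10⁻⁶.
- Right side: 6.183 × [0.0021388 × 0.99786/3,846 + 0.00025997 × 0.99974/16,154] = 6.183 × 5.71 × 10⁻⁷ = 3.53 × 10⁻⁶.

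So λ = 8.23, which is the printed 8.2. The formula likewise returns 3.00 for seizure 0-4 and 3.38 for A-fib 5-19, as printed.

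**Step 2: exact power on the same inputs.** Exposed events are Poisson with mean E·n·p2·IRR and unexposed events Poisson with mean (1−E)·n·p2. Given the total, the test rejects when the exposed count reaches the one-sided 5% critical value of a binomial with probability E. For SVT 0-4 the means at IRR 8.2 are 1.00 × 8.2 = 8.2 exposed and 4.2 unexposed. Power is summed over the Poisson total.

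| Cell | Background exposed events | Formula IRR | Printed IRR | Exact power at printed | Exact power at unrounded formula value | IRR with 80% exact power |
|---|---|---|---|---|---|---|
| SVT 0-4 | 1.0 | 8.23 | 8.2 | 92.9% | 93.0% | 6.2 |
| A-fib 5-19 | 4.0 | 3.38 | 3.4 | 88.3% | 88.0% | 3.0 |
| Seizure 0-4 | 5.0 | 3.00 | 3.0 | 88.0% | 87.9% | 2.7 |
| SVT 5-19 | 13.5 | 2.02 | 2.1 | 88.6% | 84.7% | 1.9 |

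**Step 3: separate sparsity from rounding.** At the unrounded formula value the excess fades as events accumulate:
- seizure 5-19 (52 background exposed events): 82.1%;
- seizure 20-64: 81.4%; seizure 65 and over (27 events): 82.3%;
- SVT 20-64: 81.8%; SVT 65 and over: 81.0%;
- A-fib 20-64 (464 events): 80.3%.

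A-fib at 65 and over goes the other way (75.3%). There p2 = 1 − exp(−2,154.3 × 6/100,000) = 0.12, and the Poisson variance exceeds the binomial variance in the formula.

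Rounding is not uniform. The formula's 2.02 is printed as 2.1 and 1.449 as 1.5 (both upward), while 8.23 is printed as 8.2. At the printed 2.1 the Annex 7 formula itself gives 84% power.

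**Step 4: source of the gap.** A pooled-variance normal formula gives 93.4% power at 8.2 for SVT 0-4, close to the exact figure. Its 80% ratio is 5.5 (6.4 with a continuity correction), against 6.2 exact. Most of the discrepancy therefore comes from the unpooled variance.

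**Step 5: effect of the discarded time.** The calculation counts all non-exposed time as unexposed. Sections 7.1 and 7.3.1 discard the time between the end of exposure and 26 weeks after dispensing. The documents do not give the usable share. Assuming 50% or 25% of the year is usable as unexposed, the 80% ratio for SVT 0-4 becomes about 7.0 or 8.4 (8.35), and power at 8.2 becomes 89% or 79%. For seizure 0-4 the 80% ratio becomes about 2.9 or 3.2.

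**The case against.** **The formula is disclosed and correctly applied.** In three of the four tabulated cells the printed figure is what Annex 7 yields, section 7.5.2 admits simplification, and section 7.9 makes its conclusion conditional on the assumptions. This stands as to transparency. It does not make the 80% label correct.

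**High power at the printed value is not confined to sparse cells.** Seizure 5-19 has 88.2% at 1.5 and SVT at 65 and over has 88.0% at 1.4. This is true, but there it is rounding: at the unrounded values the figures are 82% and 81%. In SVT 0-4, seizure 0-4 and A-fib 5-19 rounding explains almost nothing.

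**The planned analysis is Poisson regression, not a conditional binomial test.** For SVT 0-4 this hardly matters, because power at 8.2 was 89-96% across conditional, score, Wald, log-Wald and likelihood-ratio tests. For A-fib 0-4 it matters greatly. A reader might infer that the printed 54.0 there has 97% power and that about 30 is the right value. The documents do not support this. That result rests on Table 8's 1.6 per 100,000, while sections 5 and 7.5.3 give 0.0016 per 1,000, which is 0.16 per 100,000. At 0.16 the exact power at 54 is about 14% and the Annex 7 ratio is about 504. Even at 1.6, a log-Wald test reaches only about 40%, because no unexposed event occurs in about 60% of samples (exp(−0.517)).

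**Replacing 8.2 by 6.2 refines one approximation and keeps an optimistic one.** This stands, as Step 5 shows, so the recalculation must handle both together.

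**Conclusion.** The stated 80% power is inaccurate in the sparse cells. On the protocol's own inputs it is about 93% for SVT 0-4 and 88% for seizure 0-4 and A-fib 5-19. The ratios with 80% power are about 6.2-6.3, 2.7 and 3.0, against the printed 8.2, 3.0 and 3.4. For SVT 5-19 exact power is 85% at the formula's 2.02 and 80% at 1.9; the printed 2.1 adds upward rounding. These results assume the protocol's rates, user numbers and time split, and a one-sided conditional test.

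The point is minor. The error is conservative, the sample is fixed and no analysis changes. A reader might infer that section 7.9's conclusions fall, or that large-sample theory as such fails in these tables. Neither follows. A ratio of about 6 is still a strong association, the youngest group remains inadequate for A-fib on either rate, and most of the gap comes from the choice of variance. Table 8 at 20-64 years, printed as 1.6 where the formula gives 1.14, is a larger discrepancy and neither sparsity nor rounding explains it.

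**What to change.** - Recompute seizure 0-4, SVT 0-4, SVT 5-19 and A-fib 5-19 by the exact conditional method or by simulating the planned Poisson model. Use unexposed time net of the discarded period up to 26 weeks, and state the share assumed.
- Restate these cells in Tables 6-8 and the 8.2 in section 7.9, and note in Annex 7 that the unpooled formula is conservative with few events.
- Reconcile 1.6 and 0.16 per 100,000 for A-fib 0-4 before giving any recomputed figure for that cell.
- Apply one rounding rule throughout; to the nearest decimal, the formula value for SVT 5-19 is 2.0.
- Correct Table 8 at 20-64 years, from 1.6 to the formula's 1.14 (1.1 to one decimal).

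The cost is a short recalculation and edits to the tables and one sentence. Data, design and analysis are untouched.

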7.10 Other Aspects

N/A

8 PROTECTION OF HUMAN SUBJECTS

This is an observational study with no administration of any therapeutic or prophylactic agent. Subjects observed in this study will continue with the normal standard of care as provided by their personal physician. Pre-existing national register data will be the sole data source. According to Danish, Finnish, Norwegian, and Swedish law, register-based studies can be carried out without consent from the data subjects where the processing takes place for the sole purpose of carrying out statistical or scientific studies of significant public importance and where such processing is necessary in order to carry out these studies. It is an absolute requirement that the publication of statistical or scientific results may never reveal the identity of individuals or otherwise compromise data subjects. We will obtain approval by the data agencies in the four countries before data management and data analyses will be performed.

9 MANAGEMENT AND REPORTING OF ADVERSE EVENTS/ADVERSE REACTIONS

This is a non-interventional database study based on secondary use of data collected for other purposes. No administration of any therapeutic or prophylactic agent is required in this protocol. No reporting of individual adverse events or product quality complaints to regulatory agencies is planned for this database study because there is no access to individual patient/subject records and it is not possible to assess the causality of individual cases. Study-specific health outcomes of interest, including any that qualify as adverse events, will be summarized as part of any interim analysis (including safety analysis, if required) and in the final study report, which will be provided to regulatory agencies by the sponsor as required.

Any relevant safety information will be summarized in the appropriate Periodic Safety Update Report (PSUR)/Periodic Benefit Risk Evaluation Report (PBRER) and/or Development Safety Update Reports (DSUR) if required.

If an investigator elects to spontaneously report any suspected adverse reactions or product quality complaints, they should be reported via fax to Local Designated Point of Contact (DPOC) (Denmark: ^{PPD} [redacted] Finland: ^{PPD} [redacted]; Norway: ^{PPD} [redacted] Sweden: ^{PPD} [redacted], in English using an AE and PQC report form (see section 12 for form) for reporting to worldwide regulatory agencies as appropriate.

10 PLANS FOR DISSEMINATING AND COMMUNICATING STUDY RESULTS

The results will be disseminated in working reports. In addition, the results will be submitted for publication in international peer-reviewed journals.

The Risk Management Subteam (RMST) Lead /Clinical Safety Risk Manager (CSRM) Physician will be notified if any safety data are generated in the final study report or any interim report. The safety and conclusion sections of the final study report or interim report must be reviewed by the RMST Lead/CSRM Physician prior to finalization of the report. The review by the CSRM Physician must occur prior to any release of results to the public domain in the form of abstracts, posters, presentations or manuscripts.

12 APPENDICIES

12.1 Annex 1 List of Stand-Alone Documents

No.	Document Reference No	Date	Title
1A.	N/A	May 2014	Number of Desloratadine Users

Documents are available upon request.

12.2 Annex 2 ENCePP Checklist for Study Protocols (Revision 4)

EUROPEAN MEDICINES AGENCY
SCIENCE MEDICINES HEALTH

EUROPEAN NETWORK OF
CENTRES FOR
PHARMACOEPIDEMIOLOGY
AND PHARMACOVIGILANCE

Doc.Ref. EMA/540136/2009

ENCePP Checklist for Study Protocols (Revision 4)

Adopted by the ENCePP Steering Group on 15/10/2018

The European Network of Centres for Pharmacoepidemiology and Pharmacovigilance (ENCePP) welcomes innovative designs and new methods of research. This Checklist has been developed by ENCePP to stimulate consideration of important principles when designing and writing a pharmacoepidemiological or pharmacovigilance study protocol. The Checklist is intended to promote the quality of such studies, not their uniformity. The user is also referred to the ENCePP Guide on Methodological Standards in Pharmacoepidemiology, which reviews and gives direct electronic access to guidance for research in pharmacoepidemiology and pharmacovigilance.

For each question of the Checklist, the investigator should indicate whether or not it has been addressed in the study protocol. If the answer is "Yes", the section number of the protocol where this issue has been discussed should be specified. It is possible that some questions do not apply to a particular study (for example, in the case of an innovative study design). In this case, the answer 'N/A' (Not Applicable) can be checked and the "Comments" field included for each section should be used to explain why. The "Comments" field can also be used to elaborate on a "No" answer.

This Checklist should be included as an Annex by marketing authorisation holders when submitting the protocol of a non-interventional post-authorisation safety study (PASS) to a regulatory authority (see the Guidance on the format and content of the protocol of non-interventional post-authorisation safety studies). The Checklist is a supporting document and does not replace the format of the protocol for PASS presented in the Guidance and Module VIII of the Good pharmacovigilance practices (GVP).

Study title:

Association between use of desloratadine and risk of seizures, supraventricular tachycardia, and atrial fibrillation or flutter: A Nordic register-based study

EU PAS Register® number: Study not yet registered**Study reference number (if applicable):** 205-00

Section 1: Milestones	Yes	No	N/A	Section Number
